across 3 racial/ethnic groups (White, Black, Hispanic). These differences will be examined in bivariate analyses (unadjusted) and multivariable analysis (adjusted). We will develop multilevel multivariable regression models to examine the association between predictors, mediators, and moderators on the primary outcome (testing uptake) and secondary outcomes (COVID mitigation practices, and family mutual aid). We will use multivariable multilevel logistic (binary outcomes) and linear (continuous outcomes) regression models to conduct cross-sectional analysis at each time point. For outcomes where statistical distributional assumptions are violated we will use the *non-parametric multilevel mixture model (NPMM)*. In this model, latent classes are extracted at multiple levels of a hierarchical data structure (e.g., individual, household) and, unlike the conventional multilevel models (MLM), there are no continuously distributed random effects.^{1,2}

Longitudinal Analysis

We will use a random-intercepts logistic (with a binary response) or linear (continuous outcome) multilevel regression model, for each timepoint t , individual i , that is a member of household j . A random-intercepts model will give the conditional assessment of the extent to which household-level exposures vary on the outcomes after taking into account individual-level exposures, assuming the household-level variation is normally and independently distributed with a constant variance. The variance partitioning coefficient (VPC), or the amount of variability in the outcome attributed to predictors at each level, will be calculated. This will tell us to which extent household level and individual-level variables contribute to the outcome allowing for an examination of the impacts of COVID-19 at multiple levels. Structural equation models (SEM) will be used to examine mediating and moderating variables in the regression analyses. In addition, we will conduct sensitivity analyses (e.g., intent to treat vs receive intervention, components of intervention received, per protocol) and subgroup analyses (e.g., race/ethnicity, gender, age, education, essential worker) based on findings from aims 1-3.

For binary outcomes, we will use a random-intercepts logistic multilevel regression model, for each timepoint t , individual i , that is a member of household j . The basic equation will follow the form:

$$y_{tij} = \ln\left(\frac{\pi_{tij}}{1 - \pi_{tij}}\right) = B_0x_{0ij} + \beta_1x_{tij} + \beta_2x_{ij} + \beta_3x_j + \varepsilon_{i(j)}^{(2)} + \varepsilon_j^{(3)}$$

For continuous outcomes, we will use a random-intercepts multilevel regression model, for each timepoint t , individual i , that is a member of household j . The basic equation will follow the form:

$$y_{tij} = B_0x_{0ij} + \beta_1x_{tij} + \beta_2x_{ij} + \beta_3x_j + \varepsilon_{i(j)}^{(2)} + \varepsilon_j^{(3)}$$

A random-intercepts model will give the conditional assessment of the extent to which household-level exposures vary on the outcomes after taking into account individual-level exposures, assuming the household-level variation is normally and independently distributed with a constant variance. Where y_{tij} represents the outcome for the i^{th} individual that resides in household j and time t , x_{tij} denotes the vector of time-varying covariates (e.g., exposure to COVID-19, household member exposed, household member infected), x_{ik} denotes the vector of individual-level variables (e.g., age, gender, race, ethnicity, comorbidities), and x_k is a vector of household-level variables (e.g., household plan developed). The vector of regression coefficients for the time-varying variables is denoted as β_1 ; similarly, β_2 denotes the vector of regression coefficients for the individual-level variables, and β_3 denotes the vector of regression coefficients for the household-level variables.

The random effect for individual i that is a member of household j is denoted by $\varepsilon_{i(j)}^{(2)}$, and $\varepsilon_j^{(3)}$ denotes the random effect for the third (household-level) cluster. We assume the random effects are independent and normally distributed [5-7]. The variance partitioning coefficient (VPC), or the amount of variability in the outcome attributed to predictors at each level, will be calculated. This will tell us to which extent household level and individual-level variables contribute to the outcome allowing for an examination of the impacts of COVID-19 at multiple levels. In order to examine these impacts, a test for the difference in two proportions using a mixed-effects regression model based on a clustered 3-Level Hierarchical Design with level-3 (household) randomization will be utilized.

Mediation, moderation, and mediated moderation, moderated mediation analyses

In mediated moderation a moderating effect is mediated, whereas in moderated mediation one or more paths in a mediation model are moderated. The intervention components are assumed to influence the mediators/moderators in addition to the outcome. These differential effects on the mediators are assumed to persist over time and influence the outcomes with the possibility of lagged effects of the mediators on the 9-month outcomes. Moderating effects will be examined using multiple group comparison strategies in SEM. This strategy fits the same model across groups and compares fit under conditions where across group equality constraints of coefficients are induced versus conditions where the solution is unconstrained. If the equality constraints adversely affect model fit, then this suggests non-equivalence of coefficients across groups. A useful feature of this analytic scheme is that it permits testing for metric equivalence across groups. This is important for making valid across group comparisons. In instances, where we seek to evaluate non-linear relational forms, we will adopt a limited information estimation approach within our SEM framework. We will create quadratic and polynomial terms and/or re-categorize variables in ways that will allow us to detect non-linear relational forms.

Handling Missing Data.

In some analyses, there is likely to be missing data due to a respondent not answering a question. In general, this occurs infrequently, but occasions may arise where missing data must be formally dealt with. Data can be missing at random (MAR), missing completely at random (MCAR) or missing in a systematic way that precludes application of simple methods of missingness, such as the Expectation-Maximization methods. To gain perspective on the nature of the missingness for a given variable, we will create a dummy variable coded for each respondent as 1 = has a missing value on the variable in question and 0 = does not have a missing value, and then test for associations between these missing data indicators and other variables in the models. We will also apply Little's multivariate test for MCAR. Ideally, missingness will not be related to other variables. Missing data also can result from study attrition. We will differentiate these two sources of missingness and explore the dynamics of each. We will approach missing data using either full information maximum likelihood methods, multiple imputation methods or systematically model missing data bias, depending on the nature of the data and the models being evaluated.

Dealing with violations of statistical assumptions.

Many traditional tests rely on maximum likelihood or least squares analytic schemes that make population level assumptions. When either theory or data suggest that the assumptions are questionable, robust estimation methods as implemented in M Plus will be used. In addition, if statistical assumptions are violated nonparametric statistical methods (as proposed above) will be used.

Outliers. We will be sensitive to outliers in all analyses. We will apply standard methods for outlier detection (e.g., analysis of leverage statistics, residuals, and dfBetas) and use graphical approaches.

Specification error. We will be sensitive to issues of specification error, being careful to explore a wide range of model diagnostics to protect against gross model misspecification.

Measurement error. Where possible, we will adopt analytic strategies that explicitly model measurement error, such as using SEM with multiple indicators. For single indicator SEM, measurement error can be modeled by fixing error variances of measures at *a priori* specified values that map onto their reliability as suggested by previous research [8,9]. If it is a multi-item measure, we can create multiple indicators using split-half methods. When we cannot formally model measurement error, we will take care to recognize biasing effects of measurement error when interpreting the results of statistical analyses.

Aim 5 is to use FDA-authorized tests, characterize the community and household epidemiology of SARSCoV2/COVID-19 including prevalence of current infection, incidence of new infection,

symptomatic illness, accessing care, hospitalization and mortality.

Analysis for Aim 5

To address Aim 5, we will estimate current infection using SARS-CoV2 RNA testing of baseline specimens from the intervention group. Incidence of new infection per 100 person-months will be estimated from the results of repeat voluntary in-home RNA and antigen testing (intervention group) and approximated from self-reported results of repeat voluntary tests in the controls. Occurrence of symptomatic illness, accessing COVID-19 care, hospitalization and mortality will be measured in both groups by self-report from family members. Qualitative methods will use a grounded theory approach in which ethnographers identify key themes for further inquiry and analyses and contribute to quantitative data triangulation.

Aim 6 is to (with our community and scientific advisory boards,) develop pilot projects that will address knowledge and implementation gaps that are uncovered as new diagnostic testing is developed and as the investigative team and community partners work together to address Aims 1-5.

Analysis for Aim 6

The analysis plans for Aim 6 will be developed for projects as appropriate.

Power and Sample Size.

Consensus has yet to be determined on the precise power calculations for multilevel models[1-3]. Subramanian and other respected scholars in multilevel modeling argue that if the purpose of the multilevel model is to estimate the variation of level-1 variables, the size of the level-1 variable is really the driving factor [2,3]. Power for the proposed study was calculated using Power Analysis and Sample Size software (PASS 2020) based on household level randomization, individual level outcomes using conservative estimates and adjusting for 15% attrition and allowing for subgroup analyses [4]. A test for the difference in two proportions using a mixed model based on a clustered 3-Level Hierarchical Design with level-3 (household) 2:1 intervention: control randomization. The total sample size of 300, obtained from 100 level-3 units (households) in the intervention group and 50 level-3 units in the control group with an average of 2 level-2 units (individuals) per level-3 unit (household) and an average of 3 level-1 units (timepoints) per level-2 unit (individual), achieves >80% power to detect a difference between the group proportions of at least 0.15. The proportion in group 2 is 0.10. The correlation of level-1 units within a level-2 unit is <0.7. The correlation of level-2 units within a level-3 unit is <0.3. A test based on a mixed-effects logistic regression is anticipated at a significance level of 0.05.

References:

2. Snijders AT. Power and sample size in multilevel modeling. 2005;3:1570-1573.
3. NCSS LLC. PASS 2020 Power Analysis and Sample Size Software; 2020. ncss.com/software/pass.
6. Robinson TJ. Multilevel Analysis: Techniques and Applications. *J Am Stat Assoc*. 2003;98(462):496-496.
7. Hox JJ. Multilevel Analysis: Techniques and Applications. Psychology Press; 2002.
8. Joreskog, K. G., & Sorbom D. (1988). PRELIS: A Program for Multivariate Data Screening and Data Summarization. A Preprocessor for LISREL. Chicago: SSI, Inc.
9. Joreskog, K. G. (1978). Structural analysis of covariance and correlation matrices. *Psychometrika*, 43, 443-477.

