### **Outcomes {12}**

The primary outcome of interest is the following:

1. Household COVID-19 testing

Household COVID-19 testing uptake at the 9-month follow-up (9MFU) will be the primary outcome of interest. Our project will document testing uptake that is either administered by nurses or self-administered during home visits in the experimental arm, as well as self-reported information regarding COVID-19 testing uptake by study participants in the treatment and control groups. Participants will be asked whether they have received COVID-19 testing in the past three months, as well as about variables collected via the COVID-19 Symptoms, Diagnoses, and Testing scale. The COVID-19 Symptoms, Diagnoses, and Testing scale is adapted from the COVID-19 Cannabis Health Questionnaire. Specifically, participants will be asked questions regarding whether they are currently sick with an illness that might be related to COVID-19, any symptoms the participant experienced in the past three months, and the result of the participant's last COVID-19 test.

The secondary outcomes of interest are:

1. Household COVID-19 Testing Uptake

All medical services delivered by nurses during home-visits (such as COVID-19 test administration) will be carefully documented by the investigative team. At the time of the 6-month-follow-up (6MFU) assessment, the project team will obtain self-reported information regarding COVID-19 testing uptake by study participants in the treatment and control groups. Respondents will be asked whether they have received COVID-19 testing in the past six months. Respondents will also be asked questions from the COVID-19 Symptoms, Diagnoses, and Testing scale regarding whether they are currently sick with an illness that might be related to COVID-19, any symptoms the participant experienced in the past six months, and the result of the participant's last COVID-19 test.

2. COVID-19 control measure uptake

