#### Data collection and management

#### **Plans for assessment and collection of outcomes {18a}**

Data will be collected at eight time-points: baseline, monthly during months 1-6 of the study, and at 9 months post-baseline. Participants will complete self-reported surveys that assess basic demographics such as birthdate, age, gender, race/ethnicity, educational attainment, etc. In addition to collecting basic demographics, the study surveys will contain items and scales from the PhenX Toolkit and the NIH Disaster Response website. These survey items and scales will assess participants' household-level

COVID-19 routine testing, household-level COVID-19 indicated testing, COVID-19 vaccine uptake, adoption of COVID-19 control measures, household-level mutual aid capacity, and seasonal influenza vaccine uptake. All survey items developed by our team will be shared with the Rapid Acceleration of Diagnostics Underserved Populations (RADx-UP) Coordination and Data Collection Center and made public. Data will be collected via tablets that will be programmed in REDCap. Surveys are available in English and Spanish to facilitate, survey data collection. The survey may be self-administered or, in the case of low literacy or lack of familiarity with electronic devices, data collection staff will read prompts and record survey responses onto the tablets. Mode of administration will be recorded for later analysis of potential bias. To reduce social desirability bias, CHWs and nurses who deliver the NCFP intervention will not take part in the data collection process. Rather, data collection will be conducted by dedicated staff who are trained in survey research methods and human subject protections, including confidentiality. Additionally, social desirability tendency will be assessed using designated items in the study surveys. Furthermore, we will record participation rates for each household by member.

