The NCFP intervention addresses this shortcoming in several ways. First, the focus of the intervention is to help mitigate COVID-19 at the household level by developing a sustained partnership between nurses, CHWs, and families to increase the uptake of feasible strategies at home. Through regular at-home visits by nurses and CHWs, families receive relevant information on how to slow the rate of COVID-19 transmission at home and be offered COVID-19 tests free of charge. The NCFP intervention also helps to create an infection control plan that is uniquely tailored to each household's circumstances. Therefore, the mitigation strategies these households practice will make a difference in minimizing the COVID-19 impact at home. Through this sustained partnership, the intervention delivery team will build a relationship with these households based on mutual trust and cooperation, so households will be more inclined to incorporate COVID-19 mitigation behavior in their daily routine.

There are a few limitations that should be considered in this trial. First, the outcome measures relied on self-reports, which may be biased on the basis of social desirability and recall. The random assignment of participants will ensure that an equal amount of social desirability will be present in both study arms; therefore, social desirability will not bias the results. The study's outcomes will also be assessed on a monthly basis to eliminate any recall bias. Second, we recruited participants in a single geographic and clinic setting, so overall generalizability to other settings should be considered. However, recruitment from Mott Haven will increase generalizability to underserved communities that have also

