A Nurse-Community Health Worker-Family Partnership Model: Addressing Uptake of COVID-19 Testing and Control Measures

Statistical Analysis Plan (SAP)

Unique Protocol ID: 3P30DA011041-23S1

Protocol Version: 1.1

NCT #: NCT04832919

Document Date: 07/12/22

Contributors:

[name] – Senior Biostatistician

[name] – Junior Research Scientist/Data Manager

STATISTICAL DESIGN AND POWER

Measures.

Definition of Primary Outcomes

Household COVID testing uptake at the 9-month follow up is one of the main primary outcomes of interest. The investigative team will document all medical services administered by nurses during home visits, as well as self-reported information regarding COVID-19 testing uptake by study participants in the treatment and control groups. Participants will be asked whether they have received COVID-19 testing in the past three months [Yes/No]. Additionally, variables collected via the COVID-19 Symptoms, Diagnoses, and Testing Scale are the primary outcomes. This questionnaire is adapted from the COVID-19 Cannabis Health Questionnaire (CCHQ) (Vidot et al, 2020) and will measure COVID-19 symptoms, diagnoses, and testing. At the 9-month follow up point, participants will be asked questions regarding whether they are currently sick with an illness that might be related to COVID-19, any symptoms the participant experienced in the past three months [Check All That Apply], and the result of the participant's last COVID-19 test [Positive/Negative].

Definition of Secondary Outcomes

For the randomized trial, data collected utilizing the following questionnaires are secondary outcomes:

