COVID-19 control measure uptake, which is adapted from the COVID-19 Knowledge, Attitudes, and Avoidant Behaviors section of the Understanding America Study (CESR, 2020). Respondents will be asked questions regarding their engagement in behaviors associated with COVID-19 exposure on a 5-point scale [Almost Never, Sometimes, a Moderate Amount of the Time, Most of the Time, Always]. Greater values indicate higher frequency of uptake of COVID-19 prevention behaviors (e.g. "Canceled or postponed social activities." "Avoided riding the bus or subway") This questionnaire also includes questions regarding their uptake of COVID-19 control measures such as PPE usage and hand washing or sanitation. This will be measured both in immediate follow up (6 months), asking the participant to recall the past six months and also in delayed follow-up (9 months), asking the participant to recall the past three months.

Household COVID-19 Testing Uptake will be assessed as above, however at the immediate follow up time point (6 months). At the 6-month follow up point, participants will be asked whether they have received COVID-19 testing in the past six months [Yes/No]. Further, the COVID-19 Symptoms, Diagnoses, and Testing Scale will be administered at six months. Questions will ask respondents whether they are currently sick with an illness that might be related to COVID-19, any symptoms the participant experienced in the past six months [Check All That Apply], and the result of the participant's last COVID-19 test [Positive/Negative].

Vaccine Uptake will be documented by the study team via seasonal influenza and COVID-19 vaccination referrals by study nurses. Investigators will obtain self-reported information and documentation of influenza vaccine uptake by participants in both treatment arms by asking participants if they have received the influenza vaccine at the 6-month and 9-month follow up assessments [Yes/No] and whether they received the COVID-19 vaccine [Yes/No], the type of vaccine, and the number of doses.

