Aim 4 is to (With our community advisors) develop, implement and test the effectiveness of a Nurse-Community Health Worker-Family Partnership intervention to increase reach, acceptance and uptake of diagnostic testing, adherence to COVID-19 prevention strategies, and development of a household mutual aid strategy to respond to COVID-19 related events within the home and community.

Analysis for Aim 4

The analysis for Aim 4 will encompass all variables of interest in Aims 1, 2, and 3 collected at baseline, six months, and nine months. Descriptive analyses will include participant and household level testing uptake, adherence to public health mitigation strategies, and household cohesion at each of the time points for the randomized controlled trial. Data will be stratified with respect to important demographic factors (e.g., age, race, gender, ethnicity). Continuous variables will be summarized using the mean, standard deviation, median, range, and interquartile range, while nominal and ordinal variables will be summarized using frequencies and percentages. Bivariate analyses will be conducted to examine associations between the outcomes of interest (testing uptake, COVID mitigation practices, and household mutual aid) and key predictors (intervention group), confounders (previous infection or vaccination), moderators (e.g., gender, age, testing fatigue), and demographic characteristics. To examine bivariate associations between continuous variables that are approximately normal or may become approximately normal after an appropriate transformation, the Student's t-test will be used. For other continuous variables where normality cannot be assumed, the Wilcoxon rank-sum test will be used instead. Chi-square tests will be used to assess group differences for nominal data. We will use Chi-square tests and the Cochran Mantel-Haenszel tests for comparison in ordinal characteristics. The Fisher's exact test will be considered for contingency tables with sparse cells. We will compare outcomes

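### The month-6 and month-9 testing items cover different windows and phases, yet the longitudinal model and power calculation treat them as repeats of one outcome with no arm-by-time term

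*SAP*

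**What the plan says.** **Look-back windows.** For the month-9 primary, the SAP (Definition of Primary Outcomes) states "Participants will be asked whether they have received COVID-19 testing in the past three months [Yes/No". For the month-6 secondary, it (Definition of Secondary Outcomes) states "participants will be asked whether they have received COVID-19 testing in the past six months [Yes/No". The protocol, Outcomes {12}, agrees on month 6: "Respondents will be asked whether they have received COVID-19 testing in the past six months". The look-back of the baseline item is not given.

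**Phase covered.** The intervention runs for five months (Protocol, Trial design {8} and Intervention description {11a}). The six-month item therefore contains all of it, and the month-9 item covers only months 7-9.

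**Analysis.** The Aim 4 (efficacy) analysis uses data "collected at baseline, six months, and nine months". Under Longitudinal Analysis: "We will use a random-intercepts logistic (with a binary response) or linear (continuous outcome) multilevel regression model", with timepoints nested in individuals and individuals in households. The same section says the difference in two proportions will be tested with a mixed model on this three-level structure. The time-varying covariates it gives as examples are COVID-19 exposure variables. No time or arm-by-time term is listed. The SAP also plans cross-sectional multilevel models at each time point, and its Framework section compares baseline with month 9.

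**Power.** The Power and Sample Size section assumes "an average of 3 level-1 units (timepoints) per level-2 unit (individual", a control proportion of 0.10 and a difference of at least 0.15. It does not say which look-back window these refer to or which three timepoints are meant. Protocol, Sample size {14}, makes the same assumptions.

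**Monthly surveys.** Protocol {18a}: "Data will be collected at eight time-points: baseline, monthly during months 1-6 of the study, and at 9 months post-baseline". The protocol Discussion says that "outcomes will also be assessed on a monthly basis to eliminate any recall bias".

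**The concern.** A repeated-measures model with one arm coefficient presumes that each visit measures the same quantity. Here it does not. Whether someone was tested at all in six months is a different event from whether they were tested in three, and the two windows fall in different phases of the trial. Month 6 captures uptake while nurses are offering tests at home; month 9 captures what persists afterwards. A single coefficient would blend the two, and a during-treatment effect could be read as success on a primary outcome that is defined after treatment.

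The plan does not say which model supplies the primary test. Its power statement rests on the three-timepoint mixed model, so that model could become the headline result. The power figure also counts information from visits other than month 9.

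**Working it through.** **1. Reproducing the stated power (>80%).** Inputs from SAP Power and Sample Size: 100 and 50 households, N = 2 people per household, M = 3 timepoints, correlations at their upper limits (0.7 within person, 0.3 within household), 0.10 v 0.25. The two-sided 5% level is from SAP Final Analysis.

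- Design effect = 1 + (M-1)(0.7) + M(N-1)(0.3) = 1 + 1.4 + 0.9 = 3.3.
- Effective control n = 50 x 2 x 3 / 3.3 = 90.9; intervention n = 181.8.
- Mean proportion = (0.10 + 2 x 0.25)/3 = 0.20.
- SE0 (pooled variance) = sqrt[0.20 x 0.80 x (1/90.9 + 1/181.8)] = 0.0514.
- SE1 (unpooled) = sqrt[0.09/90.9 + 0.1875/181.8] = 0.0450.
- Power, pooled variance = Phi[(0.15 - 1.96 x 0.0514)/0.0450] = 86.4%.
- Power, unpooled = Phi[0.15/0.0450 - 1.96] = 91.6%.
- With 15% of households lost (42.5 control): 79.8% and 86.8%.

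The stated figure is reproduced.

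**2. Power for month 9 alone.** With M = 1 the design effect is 1 + 0.3 = 1.3, and 0.10 and 0.25 are taken as three-month rates.

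| | Effective control n | Pooled variance | Unpooled |
|---|---|---|---|
| No attrition | 100/1.3 = 76.9 | 79.6% | 86.6% |
| 15% attrition | 85/1.3 = 65.4 | 72.2% | 80.8% |

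If 0.10 and 0.25 were six-month rates, then with independent periods the three-month rates would be 1 - sqrt(0.90) = 0.051 and 1 - sqrt(0.75) = 0.134, a difference of 0.083. Month-9 power would be 48% (pooled variance) or 60% (unpooled), and 41% or 53% with 15% attrition.

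**3. Effect of window length alone.** Assume 0.10 v 0.25 in each three-month period, with unchanged behaviour. With correlation r between a person's two consecutive periods, P(any test in six months) = 2p - [p^2 + r p(1-p)].

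| r | Control | Intervention | Difference | Odds ratio |
|---|---|---|---|---|
| 0 | 0.20 - 0.01 = 0.190 | 0.50 - 0.0625 = 0.4375 | 24.8 points | 3.32 |
| 0.7 | 0.20 - (0.01 + 0.063) = 0.127 | 0.50 - (0.0625 + 0.13125) = 0.306 | 17.9 points | 3.03 |

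The three-month difference is 15 points, odds ratio 3.00. The plan caps the correlation between timepoints at 0.7; applying that cap to consecutive three-month periods is an assumption.

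**4. Effect confined to months 1-5.** Convert the same rates to independent monthly probabilities: control 1 - 0.90^(1/3) = 0.0345, intervention 1 - 0.75^(1/3) = 0.0914. Let the intervention arm revert to the control rate from month 6.

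- Month 6: intervention 1 - (0.9086^5 x 0.9655) = 0.402; control 1 - 0.9655^6 = 0.190; difference 21.2 points.
- Month 9: both arms 0.10; difference 0.
- Equal-weight average of the two visits: 21.2/2 = 10.6 points.

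A logistic model does not weight visits in exactly this way. The average shows the direction and rough size of the problem.

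**The case against.** The windows look deliberate. Both documents define month 9 as primary and month 6 as a separate secondary outcome. For the household scale, the SAP explains that the three-month recall is there to cover the gap between the two follow-ups. At any one visit both arms answer the same item. The cross-sectional contrasts at months 6 and 9 are therefore not biased by the mismatch, and the SAP plans them. The longitudinal equation is offered as a basic form with example covariates; even arm is not listed, so time and arm-by-time are unstated rather than excluded. All of this stands, and it confines the point to the longitudinal model and the power calculation. It does not remove the point, because no section makes the month-9 contrast the primary test.

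Several stronger readings are tempting but not supported:

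- **That the monthly surveys go unused.** Protocol {20a} plans a descriptive examination at months 1-6 and cross-sectional analysis at each time point. What can be said is that the SAP's efficacy analysis names only baseline, 6 and 9 months. The SAP's remark that assessments are infrequent explains expected low attrition, not the choice of timepoints.
- **That recall error differs by arm.** This is conjecture. Tests given at home visits are also documented by the study team, so they do not rest on recall alone.
- **That 0.10 cannot hold at both visits.** This needs constant rates, and the plan does not say which window 0.10 describes.
- **That the month-6 outcome must be rebuilt from the monthly surveys.** This would redefine a secondary outcome specified in both documents. It also depends on a monthly item whose wording and look-back are not given.

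**Conclusion.** The point holds for the longitudinal model, the test of two proportions built on it, and the power calculation. As written, these treat testing over six months during treatment and testing over three months after it as repeats of one outcome. A single arm effect across visits does not estimate the 9-month primary. Under the illustrative rates it could show about 11 points where the primary effect is nil.

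If the effect persists, the size is less certain. The window change alone moves 15 points to somewhere between 17.9 and 24.8. On the odds-ratio scale, which the logistic model uses, the shift is small (3.00 to between 3.03 and 3.32). The more serious problem is therefore the mixing of phases. All these figures rest on assumed rates and, at the two ends of the range, on independent periods or a correlation of 0.7.

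Separately, the protocol's statement that monthly assessment removes recall bias cannot hold for the primary outcome, because no survey falls between months 6 and 9.

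**What to change.** 1. **SAP, Longitudinal Analysis.** Add categorical time and arm-by-time to the model. Name the month-9 arm contrast from that model as the primary test, report month 6 as its own secondary contrast, and state that no arm effect pooled across visits will be used for efficacy. State the look-back of the baseline item too.
2. **SAP, Power and Sample Size, and Protocol, Sample size {14}.** Say which window 0.10 and 0.15 refer to, and restate power for the month-9 contrast using the figures in step 2 of the working.
3. **Protocol, Discussion.** Correct the statement on recall bias so that it does not extend to the month-9 outcome.
4. **Optional sensitivity analysis.** If the monthly item allows it, derive any test in months 4-6 from the monthly surveys. Keep the six-month item as the defined secondary outcome. Missed monthly surveys would need a handling rule.

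The cost is revised wording, a little more analysis work and a slightly less favourable stated power. No new data collection is needed.
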